#### **Analysis Dataset:**

This objective will be analyzed for all subjects in the attempted implant set.

## 2. Valve performance parameters at 30 days by transthoracic echocardiography (TTE)

#### Hypothesis/Decision criteria:

No specific hypotheses or pass/fail criteria have been set. The analysis will be descriptive, and no statistical hypothesis test will be performed.

#### Endpoint Definition/Parameters to Be Estimated:

Valve performance parameters at 30 days by transthoracic echocardiography (TTE) include:

- Mean aortic gradient
- Effective orifice area
- Degree of aortic regurgitation (transvalvular, paravalvular, total)

#### Data Collection and Analysis Method:

Each individual parameter will be collected in the ECHO CORE Lab CRF at 30-days post procedure.

For mean gradient and effective orifice area, the descriptive statistics (mean, median, standard deviation, minimum, maximum and interquartile ranges) will be presented.

Degree of aortic regurgitation will be reported as proportions at 30 days post procedure.

#### Analysis Dataset:

[figure not shown]
This objective will be analyzed for all subjects in the implanted set.

#### 7.10.5 **Other Outcome Measures**

#### 1. Event rates of the following TAVI-related complications:

Revision 3.0

Page 21 of 23

- change to surgery
- o need for cardiopulmonary mechanical assistance
- coronary occlusion or obstruction
- annular rupture or dissection
- ventricular perforation
- mitral valve damage
- prosthetic valve displacement, migration, or embolism
- acute kidney injury (up to 7 days post procedure)

#### Data Collection and Analysis Method:

Event rate estimates for each of the above TAVI-related complications will be provided at 30 Days, 6 months, 1 year and annually through 5 years for the attempted implant set. The outcome is descriptive including Kaplan-Meier rates and no statistical hypothesis test is specified.

#### 2. All-cause mortality at 6 months, one year, and annually through 5 years

Event rate estimates will be provided at 6 months, 1 year and annually through 5 years for the attempted implant set. The outcome is descriptive including Kaplan-Meier rates and no statistical hypothesis test is specified.

#### All stroke (disabling and non-disabling) at 6 months, one year, and annually through 5 years

Event rate estimates will be provided at 6 months, 1 year and annually through 5 years for the attempted implant set. The outcome is descriptive including Kaplan-Meier rates and no statistical hypothesis test is specified.

#### 4. Myocardial infarction at 30 days, 6 months, one year, and annually through 5 years

Event rate estimates will be provided at 30 days, 6 months, 1 year and annually through 5 years for the attempted implant set. The outcome is descriptive including Kaplan-Meier rates and no statistical hypothesis test is specified.

#### 5. Life-threatening bleeding at 30 days, 6 months, one year, and annually through 5 years

Event rate estimates will be provided at 30 days, 6 months, 1 year and annually through 5 years for the attempted implant set. The outcome is descriptive including Kaplan-Meier rates and no statistical hypothesis test is specified.

## 6. New AV-Conduction disturbances (LBBB and RBBB) at 30 days

Event rate estimates will be provided at 30 days for the attempted implant set. The outcome is descriptive including proportion rates and no statistical hypothesis test is specified.

#### 7. Prosthetic valve endocarditis at 30 days, 6 months, one year, and annually through 5 years

Event rate estimates will be provided at 30 days, 6 months, 1 year and annually through 5 years for the attempted implant set. The outcome is descriptive including Kaplan-Meier rates and no statistical hypothesis test is specified.

Revision 3.0

Page 22 of 23

#### 8. Prosthetic valve thrombosis at 30 days, 6 months, one year, and annually through 5 years

Event rate estimates will be provided at 30 days, 6 months, 1 year and annually through 5 years for the attempted implant set. The outcome is descriptive including Kaplan-Meier rates and no statistical hypothesis test is specified.

9. Valve-related dysfunction, defined as moderate or severe prosthetic valve stenosis, or moderate or severe prosthetic regurgitation (per VARC II) at one year and annually through 5 years

Event rate estimates will be provided at 1 year and annually through 5 years for the implanted set. The outcome is descriptive including proportion rates and no statistical hypothesis test is specified.

10. Valve-related dysfunction requiring repeat procedure at 30 days, 6 months, one year, and annually through 5 years

Event rate estimates will be provided at 30 days, 6 months, 1 year and annually through 5 years for the attempted implant set. The outcome is descriptive including Kaplan-Meier rates and no statistical hypothesis test is specified.

- 11. Valve hemodynamic performance metrics by Doppler echocardiography at one year and annually through 5 year
  - a. Mean aortic gradient
  - b. Effective orifice area
  - c. Degree of aortic regurgitation (transvalvular, paravalvular, total)

The echocardiographic measurements will be reported at 1 year and annually through 5 years for the implanted set with site-reported echocardiographic data. No statistical hypothesis test is specified.

For mean gradient and effective orifice area, the descriptive statistics (mean, median, standard deviation, minimum, maximum and interquartile ranges) will be presented.

Degree of aortic regurgitation will be reported as proportions.

12. New York Heart Association (NYHA) functional classification at 30 day, 6 months, one year and annually through 5 years

[figure not shown]
NYHA classifications will be summarized with frequencies and percentages at 6 months, one year and annually through 5 years. All attempted implant subjects with available NYHA collections (I/II/III/IV) will be included in the analysis. No statistical hypothesis test is specified.

13. Post-operative EQ-5D quality of life at 30 days and one year

EQ-5D will be summarized with means, medians, standard deviations, minimums, maximums, and interquartile ranges, at 30 days and 1 year for the attempted implant set. No statistical hypothesis test is specified.

Revision 3.0

Page 23 of 23

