9.1.5.6. Estimated participation duration of each subject

Each implanted subject whether in the roll-in or primary study population will be followed up to 5 years post-procedure. Subjects who are taken to the procedure room for implantation but do not receive an Evolut PRO for any reason will be exited from the study within 30-days post the date of implant procedure unless a study system and/or implant procedure related Adverse Event (AE) is identified. If a study system and/or implant procedure related AE is identified, the subject will be followed until the event is resolved or no further actions need to be taken.

In the rare event the Evolut PRO TAV is explanted from the subject, their participation in the study ends following discharge from the explant hospitalization or 30 days post-explant (whichever comes later) to assess safety and then terminated from the study.

MDT18065EVR009 Version 5.006-Oct-2023

Page 31 of 121

Medtronic

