9.1.6.1. Description of the efficacy parameters

The efficacy parameters of aortic regurgitation and hemodynamic performance will be evaluated post-transcatheter aortic valve implantation (TAVI) and at follow-up to assess valve durability and dysfunction. The composite endpoint of device success evaluates procedural mortality, positioning of the prosthetic valve in the proper anatomical location and performance of the prosthetic valve.

9.1.6.2. Selection of method and time for evaluation, recording and analysis of the efficacy parameters

Efficacy is evaluated by the status of primary endpoint and secondary endpoints related with efficacy. The efficacy endpoints were selected per the Valve Academic Research Consortium-2 (VARC II) recommendations¹. The primary efficacy endpoint is the percentage of evaluable echocardiograms with moderate or severe aortic regurgitation at 30 days. Secondary efficacy endpoints are device success evaluated prior to discharge (at 24 hours to 7 days post-procedure) and hemodynamic performance at 30 days. Statistical analysis of the efficacy parameters were performed when the Implanted set (i.e., subjects who are implanted with the Evolut PRO, defined as the Evolut PRO is placed in the aortic annulus and completely released from the delivery catheter system) completed their 30-day follow-up evaluation. Table 3 outlines the timing of the evaluations to assess the efficacy parameters.

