#### 5. **Investigation Plan**

This is a prospective, single arm, multi-center, interventional, post-market study. Subjects will be consented for follow-up through 5 years. The enrollment phase of the study was completed; the estimated total duration of the study (first subject enrolled to last subject completing his/her last followup visit) is estimated to be 6.5 years, excluding the time required for preparing the study start-up, final report and study closure.

The study will be conducted at approximately 6 centers with a maximum of 8 centers in China with approximately 65 subjects with a maximum of up to 70 subjects with an attempted implant using the Evolut PRO system. There is no minimum number of subjects required for each clinical institution. No site will implant more than 20 subjects, excluding the roll-in subjects, without prior authorization from Medtronic. By completion of the enrollment phase, 58 attempted implanted subjects from 4 activated sites were enrolled.

Subjects who are taken to the procedure room for implantation but do not receive an Evolut PRO for any reason will be exited from the study within 30-days post the date of implant procedure unless a study system and/or implant procedure related Adverse Event (AE) is identified. If a study system and/or implant procedure related AE is identified, the subject will be followed until the event is resolved or no further actions need to be taken. In the rare event the Evolut PRO TAV is explanted from the subject, their participation in the study ends following discharge from the explant hospitalization or 30 days post-explant, or through resolution of potential related adverse events (whichever comes later) to assess safety and then terminated from the study.

Estimating 65 subjects with a maximum of up to 70 subjects in China with an attempted implant, comprised of the following:

- 1) Primary study population: 50 subjects with an attempted implant using the Evolut PRO system
- 2) Roll-in population: The first two attempted subjects at each site will be considered "roll-in" subjects. The maximum number of roll-in subjects among all sites will be 20 subjects. The roll-in population will be followed per the same protocol as the primary study population; however, results from the roll-in population will be analyzed separately from the primary study population.

[figure not shown]

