# 7.4 Handling of Missing, Unused, and Spurious Data and Dropouts

Every effort will be undertaken to minimize missing data. In time-to-event outcomes, drop-outs will be censored at the time of discontinuation, consistent with the Kaplan-Meier approach.

Unless otherwise specified in each objective, no statistical techniques will be used to impute missing data for continuous or categorical outcomes. If a subject's data are missing for any reason, that subject will not be included in that portion of the analysis. Erroneous (i.e., incorrect including withdrawal and drop out) and abnormal data will be cleaned prior to performing the database snapshot for the statistical analyses. The number of subjects included in each analysis will be reported so that the reader can assess the potential impact of missing data. Sensitivity analysis will be conducted for primary endpoints.

In the case of partial dates, if only the month and year are known, the event or assessment will be analyzed as if it occurred on the 15th of that month. If only the year is known, the event or assessment will be analyzed as if it occurred on June 30th of that year. These resolutions of partial dates are subject to all the reasonable restrictions, for example, pre-procedure events and assessments must occur between the enrollment date and the procedure date, post-procedure events and assessments must occur no earlier than the procedure date, and AE awareness date must be on or later than AE onset date.

Revision 3.0

Page 15 of 23

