## 7.5.2 Echocardiographic Data After Reinterventions

Unless otherwise specified, echocardiographic data collected after reinterventions will be excluded from all analyses, as the reported data is not associated with the implanted index valve's performance.

At the time of the primary endpoint analysis, no reinterventions occurred in any subjects prior to the 30 day visit and the primary endpoint analysis included all available echos.

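### SAP 7.10.5 item 9 does not state its numerator or denominator, and no planned measure gives the cumulative proportion of index valves that became dysfunctional by 5 years

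*SAP*

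**What the plan says.** Item 9 of SAP 7.10.5 covers prosthetic stenosis or regurgitation that is at least moderate. Its analysis text is two sentences: "Event rate estimates will be provided at 1 year and annually through 5 years for the implanted set" and "The outcome is descriptive including proportion rates and no statistical hypothesis test is specified". The neighbouring event outcomes (items 7, 8 and 10) are reported by Kaplan-Meier.

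Three rules elsewhere bear on item 9:

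- **SAP 7.5.2:** "echocardiographic data collected after reinterventions will be excluded from all analyses". This is a default that an individual analysis may override. Item 9 does not override it.
- **SAP 7.4:** there is no imputation, and when a subject's data are missing, "that subject will not be included in that portion of the analysis".
- **Explant:** Protocol 9.1.5.6 says "In the rare event the Evolut PRO TAV is explanted from the subject, their participation in the study ends" after a short safety period, and SAP section 5 says much the same.

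The nearest cumulative measure is item 10, "Valve-related dysfunction requiring repeat procedure at 30 days, 6 months, one year, and annually through 5 years", by Kaplan-Meier in the attempted implant set. Protocol 9.1.6.1 says that the follow-up evaluation of regurgitation and haemodynamics is there "to assess valve durability and dysfunction".

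**The concern.** Dysfunction is read from echo (Protocol Appendix V, section 3.0, note 4). Under the three rules, a subject whose index valve failed and was then reintervened or explanted has no usable echo at later visits. That subject drops out of item 9 because of the outcome that item 9 measures. If the failure was found between annual visits and treated before the next one, it need not appear in item 9 at any visit.

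At stake is the reading of 5-year durability. A reader who wants the share of index valves that became dysfunctional will look to items 9 and 10, and neither gives it. Item 9 leaves out treated failures at later visits. Item 10 leaves out dysfunction that did not lead to a procedure.

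**Working it through.** The documents give no dysfunction or reintervention rate after 30 days and no number implanted, so there is no plan figure to reproduce. The direction can be proved. The size can only be illustrated.

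**1. What item 9 estimates.** The words for proportions, the annual time points and the contrast with the Kaplan-Meier items point to a visit-by-visit proportion. With SAP 7.5.2, SAP 7.4 and exit after explant, the denominator is subjects with an evaluable, un-reintervened index valve. This is inferred, because the SAP does not write it out. SAP 7.10.4 shows a different treatment: for device success, a subject with a missing component stays in as a failure if another component is known to have failed. Item 9 has no such rule.

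**2. Direction among otherwise assessable subjects.** Let n be the subjects otherwise assessable at a visit, d those with current dysfunction, and r those already reintervened or explanted for dysfunction.

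- Item 9 as read: d/(n − r)
- Counting the r subjects as failures: (d + r)/n

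Cross-multiplying, d/(n − r) ≤ (d + r)/n exactly when r(n − d − r) ≥ 0. That always holds, since d + r cannot exceed n. So the exclusion lowers the rate or leaves it unchanged.

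**3. Illustration.** Assume n = 40, which is the 50 attempted implants (Protocol 9.1.5.7) less 20%, the upper limit on attrition in Protocol 10.4. The values of d and r are assumptions.

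| d | r | Item 9 as read | Counting r as failures |
|---|---|---|---|
| 2 | 0 | 2/40 = 5.0% | 2/40 = 5.0% |
| 2 | 1 | 2/39 = 5.1% | 3/40 = 7.5% |
| 2 | 2 | 2/38 = 5.3% | 4/40 = 10.0% |
| 2 | 3 | 2/37 = 5.4% | 5/40 = 12.5% |
| 0 | 3 | 0/37 = 0% | 3/40 = 7.5% |

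Item 9 hardly moves as treated failures accumulate. The gaps are within its sampling error: the exact 95% interval is 0.7% to 18.2% for 2/37, and 0% to 9.5% for 0/37.

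**4. Against a cumulative proportion over all implanted subjects, the direction is not fixed.** Take 50 implanted (the most possible) and D deaths free of dysfunction. Item 9 is d/(50 − D − r) and the cumulative proportion is (d + r)/50.

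- d = 2, r = 3, D = 10: 2/37 = 5.4% against 5/50 = 10.0%.
- d = 4, r = 1, D = 10: 4/39 = 10.3% against 5/50 = 10.0%, so the order reverses.
- d = 2, r = 1: the order reverses only from D = 16, at 2/33 = 6.06% against 3/50 = 6.00%.

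**5. Items 9 and 10 over time.** Assume yearly hazards of 0.02 for dysfunction and 0.05 for death or exit, with a share q of new cases reintervened before the next scheduled echo. Five-year cumulative dysfunction is (0.02/0.07)(1 − e^(−0.35)) = 8.4%.

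| q | Item 9 at year 5 | Item 10 event (q × 8.4%) | Cumulative dysfunction |
|---|---|---|---|
| 25% | 7.5% | 2.1% | 8.4% |
| 50% | 5.1% | 4.2% | 8.4% |
| 75% | 2.6% | 6.3% | 8.4% |

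Neither item alone gives 8.4%. With a death or exit hazard of 0.10 and q = 25%, item 9 is 7.7% against a cumulative 7.5%, so the gap nearly vanishes and changes sign.

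**6. Can items 9 and 10 be added?** No. They differ in analysis set (implanted, attempted), estimator and time basis. Item 10 counts any valve dysfunction needing a repeat procedure (Protocol Appendix V, section 1.0), without the severity threshold of item 9. One subject can also appear in both at different times.

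**The case against.** The strongest reply is that this is a choice of estimand. Dysfunction among index valves still in place is a legitimate quantity, and the SAP 7.5.2 exclusion is sensible because echos after a reintervention do not describe the index valve. Protocol 9.1.1.4 lists items 9 and 10 separately and promises no composite. All of that stands, so the exclusion should be kept.

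Much is also reported already. Item 10 shows treated dysfunction cumulatively. A failure seen on a scheduled echo before treatment counts in item 9 at that visit. SAP 7.4 requires the number analysed to be given, and Protocol 9.2.6 requires the reason for discontinuation, including explant, to be documented. A reader might infer that the plan hides failed valves; it does not. What is missing is a combined measure, and a count of how many subjects left item 9 because of prior reintervention or explant.

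A reader might also infer that the SAP expressly removes treated failures from item 9, or that item 9 must understate cumulative dysfunction. The documents support neither. The removal follows from general rules applied to an item that defines no numerator or denominator, and step 4 shows that deaths can reverse the cumulative comparison.

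Finally, explant is described as rare, and SAP 7.5.2 reports no reintervention before the 30-day visit. The effect may therefore be small.

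**Conclusion.** The point holds as a low-cost improvement to interpretation. Item 9 is under-defined. On its most natural reading, index valves that failed and were treated leave both numerator and denominator at later visits. Among otherwise assessable subjects, that can only lower the rate or leave it unchanged compared with counting them as failures. No planned measure gives the cumulative proportion of index valves that became dysfunctional by 5 years.

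The size is unknown. The illustrated gaps range from nothing to about 7.5 percentage points, rest wholly on assumed counts and lie within sampling error. The conclusion rests on reading item 9 as a visit-by-visit proportion; if a cumulative proportion is meant, the SAP should say so. No test is involved, and the 30-day endpoints are unaffected.

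**What to change.** Keep the SAP 7.5.2 exclusion. In SAP 7.10.5:

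1. Define item 9 as the proportion at each scheduled visit, among subjects with an evaluable, un-reintervened index valve, whose echo shows at least moderate stenosis or regurgitation. Use scheduled echos only, and cross-refer to item 10.
2. At each visit, report how many subjects are excluded for prior reintervention or explant, split into stenosis or regurgitation versus another reason. The split is needed because the definition of reintervention in Protocol Appendix V, section 2.0, is not limited to those two causes.
3. Add one supplementary descriptive analysis in the implanted set: cumulative incidence through 5 years of the first of (a) at least moderate stenosis or regurgitation on echo, or (b) reintervention or explant for stenosis or regurgitation, with death as a competing event. Date an echo-detected event at the echo that first shows it. Count unscheduled echos before a reintervention here only, since Protocol 9.2.5 leaves unscheduled assessments to the investigator's discretion. State how reintervention or explant for another reason is handled.

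Record the addition in SAP 7.13, which currently says that the SAP and protocol analyses are aligned.

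The cost is SAP wording, one extra descriptive analysis, and attribution of each reintervention or explant to a cause. No new visits are needed: annual echos are already scheduled, and Protocol 16.6 already asks sites for source documents on every intervention on the valve. The reported figure may be less favourable than item 9 alone.

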## 7.11 Safety Evaluation

A Clinical Events Committee (CEC) will provide independent medical review and adjudication of adverse event data used in the endpoint assessment of the investigational device. The CEC will adjudicate all deaths, and all endpoint related events reported by the investigators. The analysis of the study endpoint data will be based on CEC adjudicated events.

## **7.12 Health Outcomes Analyses**

No health outcomes analyses are planned for this study.

## 7.13 Changes to Planned Analysis

The planned analyses in this SAP are aligned with the planned analyses noted in the CIP.

#### 8. Validation Requirements

Level 1 validation (independent validation) will be used for the analysis datasets and the primary endpoints. For the primary endpoint analysis during the pre-market phase, Level 1 or 2 validation (peer review) will be used for additional analyses, data summaries, and listings within China CRO team, while the Medtronic statistician and/or programmer will do an independent level 1 or 2 validation.

#### **Statistical Appendices** 10.

There are no statistical appendices for this study.
